1.6. Current Therapeutic Options for Stage-1 HAT

Pentamidine is the only drug currently used to treat stage-1 HAT due to *T. b. gambiense*. It was introduced into the therapeutic armamentarium in 1940. The most common dosing regimen is a single daily dose via intramuscular injection for 7 days. Pentamidine is available to mobile teams in the field who, after detecting patients with stage-1 HAT, administer the first injection and assign the remaining injections to the village nurses. Pentamidine is much better tolerated than melarsoprol, however, it still has non-negligible adverse effects, including post-injection orthostatic hypotension, the risk of sterile abscess at the site of the intramuscular injections, gastrointestinal disturbances and, less frequently, renal toxicity and diabetes.

Children with stage-1 HAT currently receive the same treatment as adults.

1.7. Investigational Product and Preclinical Data

Fexinidazole is 2-substituted 5-nitroimidazole, formulated for oral administration. Fexinidazole has been shown to possess *in vitro* and *in vivo* activity against both parasites, *T.b. rhodesiense* and *T.b. gambiense*. In mouse models of both acute and chronic infection (the latter mimicking stage-2 disease), oral administration of fexinidazole at doses of 100-200 mg/kg/day was shown to be curative and to significantly prolong survival (30). Preclinical pharmacokinetic (PK) studies have indicated that oral fexinidazole is well absorbed and is widely distributed throughout the body, including in the brain (15).

In all animal species studied, fexinidazole was rapidly metabolised through oxidation, resulting in the formation of at least two active metabolites, fexinidazole sulfoxide (M1) and fexinidazole sulfone (M2), which have a trypanocidal activity similar to that of the parent molecule, and account for most of the pharmacodynamic activity. Toxicological studies were performed, including safety pharmacology and 4-week repeated-dose toxicokinetic studies in rats and dogs. In both species, 200 mg/kg/day was considered as the no observed adverse effect level (50). Fexinidazole was well tolerated up to 800 mg/kg/day, and no major toxicity was identified. While fexinidazole, like many nitroheterocycles, was shown to be mutagenic in the Ames test, it is not genotoxic to mammalian cells *in vitro* or *in vivo*, and is therefore not expected to pose a genotoxic risk in humans (50).

1.8. Safety and Tolerability in Healthy Volunteers

Fexinidazole has been investigated in three phase-I studies in healthy volunteers of sub-Saharan African origin (15). In all three studies, the subjects were closely monitored, with physical examinations, vital signs, electrocardiogram (ECG) and safety laboratory tests, as well as pharmacokinetic sampling performed before, during and after dosing. A total of 118 subjects were randomised in these studies. Single doses ranged from 100 mg to 3600 mg, and multiple doses from 1200 mg to 3600 mg for a maximum of 14 days.

Administration of fexinidazole in healthy volunteers was safe when given as a single dose or as repeated doses for 14 days. As with all nitroimidazole drugs, fexinidazole primarily affects the central nervous system (CNS) and gastrointestinal system, and can cause headache and/or vomiting or other mild to moderate gastrointestinal symptoms. At the highest dose, two subjects experienced prolonged anxiety with an episode of panic attack, associated with nausea and vomiting. No specific treatment was needed. Both subjects returned to normal within 2 to 3 days after stopping the investigational product (IP).

Fexinidazole is highly metabolized. As expected with this pharmacological class, a marked, transient, quickly reversible increase in liver enzymes was observed in one volunteer just after treatment at the highest dose for 14 days. These abnormalities were not observed in volunteers exposed to fexinidazole for 10 days. Data from these studies also suggest that there is a relationship between the dose used, as well as overall exposure (dose and duration), and the frequency and severity of abnormalities on liver function tests.

Another important laboratory finding was an increase, within the normal range, in plasma creatinine levels in subjects receiving the active treatment. This effect was not dose-dependent and is believed to be related to inhibition of renal tubular creatinine secretion, an effect that has previously been reported with nitroimidazole drugs (21). It is always reversible and is not accompanied by any other abnormalities on kidney function tests.

ECG recordings in studies in humans showed a limited number of cases of QTcFinterval prolongation, usually in the 30-millisecond range. QT interval corresponds to the time it takes for the left and right heart ventricles to depolarise (Q wave) and to repolarise (T wave). It is a fundamental marker in electrophysiology and in pharmacology. QT interval is corrected using a mathematical formula to take into account the heart rate (QTcF for the Fridericia formula). If the interval is abnormally prolonged or shortened, there is a risk of developing ventricular arrhythmia. In earlier studies, only one out of more than 4000 ECG recordings showed an increase of 60 ms compared to baseline. The absolute value remained within the normal range (<450 ms), however, a 24-hour Holter recording showed a mean QTcF-interval prolongation of 16 ms compared to baseline. The prolongation was not accompanied by any clinical signs and appeared to be present from the time of staring treatment.

1.9. Pharmacokinetics and Metabolism in Healthy Volunteers

Fexinidazole is well absorbed by the oral route, and rapidly metabolised to the sulfoxide (M1) and sulfone (M2), which account for the largest proportion of drug exposure, regardless of the dose used. Elimination of the second active metabolite is a slow process. C_{max} values for both fexinidazole and M1 are reached in 3 to 6 hours, while M2 levels peak at approximately 24 hours. The mean elimination half-life of fexinidazole and M1 is approximately 10 hours versus approximately 24 hours for M2.

Plasma levels of fexinidazole, M1 and M2 increase in a non-dose-proportional manner with no major changes in their pharmacokinetic profiles.

Urinary excretion of unchanged fexinidazole, M1 and M2 is very low. Fexinidazole, M1 and M2 together account for only 3% of the total dose.

The effects of concomitant intake of food were assessed in two separate studies. In the first study, administration after a standard high-fat meal (FDA recommended) was compared to administration under fasting conditions, and in the second study, two different field meals, i.e. Plumpy'Nut^{®1}, and a traditional meal of rice and beans, were compared to administration under fasting

¹ Peanut-based paste in a plastic wrapper for the treatment of severe acute malnutrition, easily available in the field.

conditions. The observed bioavailability of fexinidazole, M1 and M2 was multiplied by approximately 4-fold with the high-fat meal, and by 2.5- to 3.0-fold with the two field meals (15).

The effect of food on the bioavailability of fexinidazole was taken into account in the design of studies in patients. Indeed, the dosing regimen provides for food intake prior to administration of the IP. This explains why it is particularly important to comply with the instructions on food intake.

1.10. Study DNDiFEX004 in Adults

The DNDiFEX004 study is entitled: "Efficacy and Safety of Fexinidazole Compared to the Combination Nifurtimox-eflornithine (NECT) in Patients with Stage-2 Human African Trypanosomiasis (HAT) due to *T.b. gambiense*: a Non-inferiority, Multicentre, Open-label, Randomised Pivotal Study"

As of 21 November 2013, 188 patients, i.e. around 125 patients receiving fexinidazole, had been randomised in the DNDiFEX004 study. No safety issues were identified on blinded data review. A total of 11 serious adverse events (SAEs) were reported, 3 of which were considered as possibly related to the IP and which resolved without sequelae. Overall, the safety profile was similar to that observed in earlier studies in healthy volunteers, and there were no treatment discontinuations. A meeting of the Data and Safety Monitoring Board (DSMB) was held. No safety issues were identified, and it was recommended to continue the study with the same design. No parasites were found in any patients at the End of Treatment (EOT) visit, based on blinded review, and no relapses were observed among 80 patients who attended their 6-month follow-up visit, with the exception of one patient whose health status had been poor at inclusion and who died shortly after leaving hospital (blind not lifted).

In the DNDiFEX004 study, fexinidazole is administered orally once daily after a meal: three 600-mg tablets per day for 4 days and then two 600-mg tablets per days for the next 6 days.

Pharmacokinetic (PK) analysis of the first 39 patients treated with fexinidazole in the DNDiFEX004 study showed that mean exposure to the M2 metabolite, the more active metabolite, in the CSF was 2.6 times higher than the minimum inhibitory concentration (MIC) used as the target value based on animal data collected in preclinical efficacy studies. Blood M1 and M2 concentrations were higher in patients than in healthy volunteers. The CSF-to-blood ratio was around 31% for M2 and 52% for M1.

Monitoring of biochemical parameters in all patients included in the DNDiFEX004 study did not show any increases in hepatic enzymes, as had been seen in healthy volunteers. As expected, a mild and reversible increase in creatinine was

observed in a small number of patients. The increases were grade < 2, and none were reported as adverse events (AEs).

Monitoring of ECG parameters showed QTcF-interval prolongation, as expected, but with no clinical repercussions or treatment discontinuations (QTcF interval < 500ms, including at peak plasma concentration).

1.11. Choice of Dosing Regimen and Dose

The progression of HAT is identical in adults and children. The choice of the dose in children was therefore based on the results of the analysis of PK/PD data from adults, i.e. healthy volunteers and patients, and on the MIC. The dosing regimen in adults is 10 days of treatment, starting with a loading dose for 4 days followed by a maintenance dose for 6 days. Effective levels of the active drug are rapidly reached using this regimen and are maintained throughout the duration of treatment. Target blood concentrations were reached in adults. Given the PK characteristics of fexinidazole and its metabolites, a similar dosing regimen, i.e. a loading dose for 4 days followed by a maintenance dose for 6 days, can be used in children.

The factors affecting the PK of fexinidazole, such as absorption and maturation of cytochromes and of flavin mono-oxygenase (the main enzyme involved in biotransformation of fexinidazole into its active metabolites), as well as other enzyme systems, are completed before 2 years of age (59). The main metabolic pathways involved in biotransformation of fexinidazole into its metabolites are therefore considered to be the same in adults and in children over 2 years of age. In addition, there is reasonably good proportionality between the dose of fexinidazole administered and the circulating levels of fexinidazole and its metabolites.

The doses of fexinidazole to be administered in children were therefore chosen with the aim of achieving the same levels of systemic exposure, based on the quantity of fexinidazole per unit of body weight. Two points were taken into account:

- Dose administered on Day 1
- Total dose of fexinidazole administered during the entire treatment period.

The main demographic features of the 125 patients (46 women and 79 men) included in the DNDiFEX004 study at the time of the present assessment were taken into account. The age of the patients ranged from 15 to 71 years with a median of 35 years.

Mean body weight was 50.35 kg [34.5-80.0] with a median of 48 kg. It is of note that 15 patients (12 women and 3 men) weighed 40 kg or less with a minimum weight of 34.5 kg.

As mentioned above, the dosing regimen in adults is 1800 mg in a single daily intake for 4 days, followed by 1200 mg in a single daily intake for 6 days, i.e. a total dose of 14,400 mg over 10 days.

Thus:

- mean dose on Day 1 of 35.7 mg/kg [22.5-52.2];
- mean total dose administered of 28.6 mg/kg/day [18-42].

Overall, male patients are heavier than female patients, and there is therefore a minor difference, i.e. less than 15%, between the mean results in men and in women: 34.8 mg/kg on Day 1 and 27.8 mg/kg/day in men versus 40.4 mg/kg and 32.3 mg/kg/day in women.

In the potential target population of the study, i.e. 29 children diagnosed with HAT during active screening activities carried out to recruit patients to the DNDiFEX004 study, the mean age was 11 years and the mean body weight was 23.4 kg [12-40]. In the NECT-Field study (60), among 65 children between 5 and 11 years of age who were included, mean body weight was 19 kg [9-32] with a median of 18 kg.

If the mean dose on Day 1 is 35.7 mg/kg and the mean total daily dose administered is 28.6 mg/kg, the dose on Day 1 should be $1071 \text{ mg} (30 \times 35.7)$ and the desired total dose administered should be $8580 \text{ mg} (28.6 \times 30 \times 10)$ for a child weighing 30 kg.

Given the usual dosing regimen and the formulations available, i.e. 600-mg tablets, the dosing regimen should be 1200 mg daily for 4 days, followed by 600 mg for 6 days, with a total dose administered of 8400 mg.

Using this dosing regimen, a child weighing 20 kg would receive:

- Dose on Day 1, 60 mg/kg, which is slightly higher than the maximum dose administered on Day 1 in the least heavy adults (52.2 mg/kg);
- Total dose: 42 mg/kg/day, which is exactly the same as the dose administered in the least heavy adults.

In conclusion, in view of the observations above and the fact that the adult the least heavy included in the DNDiFEX004 study weighed 34.5 kg, the dosing regimen is as follows:

- Body weight between [20-35] kg:
 - o 1200 mg from Day 1 to Day 4
 - \circ 600 mg from Day 5 to Day 10
- Body weight \geq 35 kg (same as in adults)
 - o 1800 mg from Day 1 to Day 4
 - 1200 mg from Day 5 to Day 10

Fexinidazole, as 600-mg tablets, will be administered orally, after a meal, i.e. within 30 minutes after the end of the meal.

1.12. Rationale for the Study Design

Based on the encouraging efficacy and safety results in adults in the on-going DNDiFEX004 study, it would appear that oral treatment with fexinidazole could be beneficial in children 6 years of age and older. The dosing regimen in children is based on the results in adults (see Section 1.11 Choice of Dosing Regimen and Dose p 27).

This cohort of patients will provide additional efficacy data and, because the levels of systemic exposure in children are similar to those observed in adults, will show that the safety profile of fexinidazole, based on the data currently available, remains favourable.

The present study will be a plug-in to the pivotal DNDiFEX004 study in adults, which means that it will be possible to compare the results in the two studies since patients will be recruited simultaneously, i.e. same centres and investigators, with a genetically homogeneous population. In the same way, it will be possible to compare patients with stage-1 HAT in the present study to patients with stage-1 HAT in Study DNDiHATFEX005.

In order to provide the results within a reasonable timeframe, the study will be open label and will include a total of 125 children 6 years of age or older with a body weight of at least 20 kg. The patients will undergo the same assessments and investigations as the adult patients in Study DNDiFEX004. Under these conditions, if there are no statistically significant differences with regard to the efficacy and safety data, the results of treatment in children will be considered to be equivalent to those in adults. Thus, the number of children needed to treat is lower than if this had been a stand-alone study.

The objective is to be able to administer fexinidazole as a single treatment to all patients with HAT, without recourse to CSF-based staging of the disease. The aim of the present study is to assess the efficacy and safety of fexinidazole in children with stage-1, early stage-2 and late stage-2 HAT, stratified into three sub-groups. The study will provide an assessment of the success rate of treatment overall and by stratum, as well allowing for comparison with historical data on pentamidine in patients with stage-1 HAT.

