Pharmacokinetic analysis of the first 39 patients treated with fexinidazole in the DNDiFEX004 study showed that mean exposure to the M2 metabolite, the more active metabolite, in the cerebrospinal fluid was 2.6 times higher than the minimum inhibitory concentration used as the target value based on animal data collected in preclinical efficacy studies. Blood M1 and M2 concentrations were higher in patients than in healthy volunteers. The cerebrospinal fluid-to-blood ratio was around 31% for M2 and 52% for M1.
In order to provide the results within a reasonable timeframe, the study will be open label and will include a total of 125 children 6 years of age or older with a body weight of at least 20 kg. The patients will undergo the same assessments and investigations as the adult patients in Study DNDiFEX004. Under these conditions, if there are no statistically significant differences with regard to the efficacy and safety data, the results of treatment in children will be considered to be equivalent to those in adults. Thus, the number of children needed to treat is lower than if this had been a stand-alone study.
The objective is to be able to administer fexinidazole as a single treatment to all patients with HAT, without recourse to CSF-based staging of the disease. The aim of the present study is to assess the efficacy and safety of fexinidazole in children with stage-1, early stage-2 and late stage-2 HAT, stratified into three sub-groups. The study will provide an assessment of the success rate of treatment overall and by stratum, as well allowing for comparison with historical data on pentamidine in patients with stage-1 HAT.
 The dosing regimen is as follows: Body weight ≥ 20 kg and < 35 kg: 1200 mg from Day 1 to Day 4 600 mg from Day 5 to Day 10 Body weight ≥ 35 kg (same regimen as for adults) 1800 mg from Day 1 to Day 4 1200 mg from Day 5 to Day 10
 The objective of the study is to assess the efficacy and safety of an oral dosing regimen involving one daily intake for 10 days in the treatment of HAT due to T.b. gambiense at stage 1 or 2 in children 6 years of age or older weighing more than 20 kg. Primary Objective To demonstrate that the success rate 12 months after the end of treatment in patients with stage-1 or stage-2 HAT is greater than an acceptable rate of 80% and consistent with a target rate of 92%.

	

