9.1. Sample Size Determination

Determination of the sample size was based on the primary analysis (see Section 9.8.1 Primary Efficacy Analysis, p 61). With a sample size of 125 patients, the probability of rejecting H_{0A} ($\pi \le 0.8$) is 97.5% if the true success rate is 92% with a one-sided type-I error of 0.025. The probability of rejecting H_{0B} ($\pi \ge 0.92$) is also 97.5% if the true success rate is 80% with a one-sided type-I error of 0.025. The statistical power achieved is slightly higher than the desired power, and the alpha value obtained is slightly lower than the desired value, due to the discrete distribution of the population. The sample size may be 126 patients who received at least one dose of fexinidazole if two patients are recruited simultaneously at the time of study discontinuation. If the sample size exceeds 126 patients, there is a risk of simultaneously rejecting both H_{0A} and H_{0B}. The sample size should not be less than 125 in order to avoid the risk of not rejecting either hypothesis.

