9.8. Efficacy Analysis

9.8.1. Primary Efficacy Analysis

Primary Efficacy Endpoint

The primary efficacy endpoint is the. success or failure, at 12 months after the final treatment intake. The patient's treatment will be a success if there is no evidence of trypanosomes in any bodily fluid, and the WBC count in the CSF is $\leq 20/\mu$ L. Patients with no parasitological evidence of relapse, but with a CSF WBC count > 20/µL or who, in the opinion of the Investigator, require rescue treatment, will be considered to be probable relapses and therefore as failures. Death due to any cause or use of rescue medication will be considered as a relapse, i.e. a failure. A patient who attends the follow-up visit at 12 months or later and who

refuses to undergo lumbar puncture, but who has no signs or symptoms of HAT and for whom the outcome was assessed as favourable at the last assessment will be considered as a probable cure, i.e. a success, unless signs of relapse are detected on any assessment up to 18 months.

Primary Analysis

The primary analysis will be performed on the ITT population.

The primary endpoint is the success or failure of treatment, as defined above.

The primary analysis of success or failure will be performed at 12 months of follow-up.

The primary test is an exact test derived from the exact confidence interval (CI) of the success rate at 12 months.

Two sets of statistical hypotheses will be tested simultaneously:

 H_{0A} : the true success rate is equal to or less than 80%, which is considered to be unacceptable.

H_{1A}: the true success rate is greater than 80%.

 H_{0B} : the true success rate is equal to or greater than 92%, which is the target or expected success rate for fexinidazole.

H_{1B}: the true success rate is less than 92%.

If H_{0A} is rejected, then the success rate is significantly greater than 80% and the estimated rate is consistent with a rate of 92%. In this case, H_{0B} is automatically accepted, but not necessarily true.

If H_{0B} is rejected, then the success rate is significantly less than the target of 92%, and the estimated rate is consistent with the unacceptable rate of 80%. In this case, H_{0A} is automatically accepted, but not necessarily true.

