If the observed success rate is equal to or greater than 87.2% (\geq 109 successes out of 125 patients), or equal to or greater than 110 successes out of 126 patients (if the sample size is equal to 126), then the study is a success since the rate is significantly greater than 80% and consistent with the target success rate of 92%.

Conversely, if the observed success rate is less than 87.2% (\leq 108 successes out of 125patients) or less than 110 successes out of 126 patients, then the study is a failure since the success rate is significantly less than the target rate of 92% and consistent with the unacceptable rate of 80%.

The unacceptable success rate of 80% is greater than the success rate of melarsoprol at 12 months, i.e. 74.8%, because the success rates of the alternative treatments, i.e. NECT and pentamidine, are considerably higher than the rate with melarsoprol, which increases the level of unacceptability.

The target or expected rate of 92% is greater than the expected value of 89% set in the pivotal study, because the success rate is evaluated at 12 months instead of 18 months (expected gain of 1.2%) and also because the success rate reported in the pivotal study is encouraging, since only one failure (a patient whose health status had been poor at inclusion) among 150 patients was observed at the EOT, and no relapses were observed among 30 patients during the 6-month follow-up period (blinded data with an allocation ratio of 2 fexinidazole for 1 NECT).

It should be noted that, in the pivotal study, a 94% success rate was expected for NECT at 18 months, and the margin of acceptable difference was set at 13%. This means that the level of the unacceptable rate for fexinidazole is81% if the success rate for NECT is truly 94%, and 80% if the success rate for NECT was 93%. This also means that the various expectations and limits are consistent across studies.

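### Equivalence of children to adults would be concluded from a non-significant difference, with no margin, interval criterion or power; the primary threshold limits the efficacy risk, but safety has no such threshold

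*Protocol*

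**What the plan says.** Section 1.12 of the protocol, and the Study Rationale in the Protocol Summary, describe the study as a plug-in to the adult study DNDiFEX004. Both state that "if there are no statistically significant differences with regard to the efficacy and safety data, the results of treatment in children will be considered" equivalent to those in adults. The next sentence draws a design consequence: "Thus, the number of children needed to treat is lower than if this had been a stand-alone study".

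The formal part of the plan is different. Under section 9.1, "Determination of the sample size was based on the primary analysis". That analysis (section 9.8.1) is a single-arm exact test. The null hypothesis is that "the true success rate is equal to or less than 80%, which is considered to be unacceptable". The rate of 92% is the one "which is the target or expected success rate for fexinidazole". Success means at least 109 of 125 (110 of 126).

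The only between-group margin in the protocol is in section 9.8.1, where, for fexinidazole against NECT in the pivotal study, "the margin of acceptable difference was set at 13"%. No margin is given for children against adults. Section 9.8.3 describes pooled models with the pivotal study and with DNDiHATFEX005 for CSF white-cell count and stage, but no test of equivalence between children and adults.

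**The concern.** A non-significant test is compatible with no difference and also with an important difference that the data are too few to show. A rule that reads it as equivalence rewards small and noisy data: the fewer the children, the more likely the favourable verdict. Here the rule is also offered as a reason for needing fewer children.

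The sentence is the protocol's stated bridge from the adult evidence to children, and it covers safety as well as efficacy. Safety is where the rule is least protected. Section 1.11 itself calculates that a 20 kg child receives 60 mg/kg on Day 1, against a maximum of 52.2 mg/kg among the adults, so similar tolerability needs to be shown with its uncertainty. A non-significant p-value cannot do that.

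**Working it through.** **Inputs from the protocol.** 125 children (sections 1.12 and 9.1). Success threshold 109/125, unacceptable rate 80%, target 92%, pivotal expectation 89% at 18 months (section 9.8.1). About 125 adults on fexinidazole at 21 November 2013 (section 1.10).

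**Assumptions.** The protocol names neither a test nor an alpha for the child-adult comparison, so a two-sided 5% Fisher exact test is assumed. The final adult number is not given, so 125 and 250 are both shown.

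**Step 1: the plan's own figure.** With X ~ Bin(125, p), P(X ≥ 109 | 0.80) = 0.0243 and P(X ≥ 109 | 0.92) = 0.978. This agrees with the stated one-sided 0.025 and 97.5%. The exact lower 95% limit at 109/125 is 80.05%. The sample size is sound for the single-arm test.

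**Step 2: efficacy.** With child successes X ~ Bin(125, p_c) and adult successes Y ~ Bin(n_a, p_a), sum P(X=x)·P(Y=y) over all (x, y) with Fisher p > 0.05. For the joint event, keep only x ≥ 109. Results are for 125 / 250 adults.

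| True adult, child rate | Non-significant | Non-significant and ≥ 109/125 |
|---|---|---|
| 92%, 87% | 81% / 69% | 52% / 50% |
| 92%, 84% | 58% / 39% | 19% / 18% |
| 92%, 82% | 41% / 23% | 7% / 7% |
| 92%, 80% | 26% / 11% | 2% / 2% |
| 92%, 79% | 20% / 8% | 1% / 1% |
| 89%, 84% | 84% / 75% | 20% / 20% |
| 97%, 90% | 48% / 24% | 48% / 24% |

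The 97% row is illustrative. The right-hand column gives the cases in which the trial succeeds and the results are also called equivalent.

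**Step 3: one outcome that passes both.** Adults 119/125 (95.2%), children 110/125 (88.0%). Fisher p = 0.066, so equivalent under the rule. The difference is 7.2 points. SE = √(0.952·0.048/125 + 0.880·0.120/125) = 0.0348, so the Wald 95% CI for the deficit is 0.4 to 14.0 points.

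**Step 4: fewer children, easier verdict.** At 92% against 82% with 125 adults, the chance of a non-significant result is 41% with 125 children, 47% with 80, 52% with 60 and 62% with 40. The smaller numbers are assumptions standing for stage-matched subsets; the protocol fixes no stratum sizes.

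**Step 5: safety.** Same enumeration, no threshold, 125 / 250 adults. Children 10% against adults 5%: non-significant in 76.5% / 59.0%. Children 20% against adults 10%: 46% / 28%.

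**Step 6: what a margin would give.** With 92% in both groups and one-sided 0.025, power = Φ(m/SE − 1.96), where SE = √(0.92·0.08·(1/125 + 1/n_a)) = 0.0343 / 0.0297. For m = 13 points: 97% / 99%. For 10 points: 83% / 92%. For 5 points: 31% / 39%. The 5- and 10-point margins are illustrative.

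**The case against.** The strongest reply is that the sentence stands only in the rationale and the summary. It is not an objective, endpoint, hypothesis or named test in section 9, and a study below 109/125 is declared a failure whatever the comparison with adults shows. That stands, and it changes the size of the problem. A reader might infer from the non-significance column alone that a deficit of 13 points would pass about one time in five. The documents do not support that as the chance of a favourable outcome: combined with the primary threshold it is about 1%.

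A reader might also infer that 125 was chosen because of the equivalence rule. Section 9.1 rests it on the single-arm analysis alone, so the remark about needing fewer children is an unsupported justification and was not the basis of the calculation.

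Nor is the comparison wholly unmatched. Section 1.12 sets stage-1 children against stage-1 patients in DNDiHATFEX005. Section 9.8.3 pools late stage-2 patients with the pivotal study and analyses 18-month success, which softens the mismatch in stage and timepoint. Section 9.9 plans adverse-event incidences with 95% confidence intervals, which would reveal imprecision. The 125 adults are an interim count from an ongoing study, so the results with 125 are the less favourable ones.

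None of this repairs the rule. The primary test asks whether success exceeds 80%; it does not ask whether children resemble adults. The pooled models do not replace the equivalence sentence, and safety has no counterpart to 109/125.

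**Conclusion.** The point holds in a limited form. The protocol states, twice, an invalid rule for concluding equivalence, and nothing in the document supplies a margin, an interval criterion or power for it. The primary decision and the sample size are unaffected.

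For efficacy the exposure is to moderate deficits. A shortfall of 5 points from 92% passes both conditions about half the time and one of 8 points slightly under one time in five, while one of 12 points passes about one time in fifty. For safety a doubling from 5% to 10% would be called equivalent in more than half of cases even with 250 adults. These figures depend on the assumed Fisher test, the adult number of 125 to 250 and the adult rate; the fault in the rule does not. At the pivotal study's 13-point margin, 125 children would give ample power, so at that margin the fault lies in the criterion and not in the number of patients. Severity: should be fixed.

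**What to change.** In the Protocol Summary and section 1.12, delete the equivalence sentence and the inference about the number of children that follows it. State instead that differences between children and adults in success rate will be reported with 95% confidence intervals at the same timepoint and by matched stage: late stage 2 against DNDiFEX004, stage 1 and early stage 2 against DNDiHATFEX005. Report safety differences with 95% confidence intervals and make no equivalence claim.

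If a claim of comparability is kept, it should rest on the confidence interval excluding a margin stated in advance and justified for children against adults on the same drug. The 13-point margin was set for fexinidazole against NECT and should not be carried over without its own rationale.

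The cost is wording and one table of intervals, with no extra patients and no change to the primary analysis. The downside is that wide intervals, especially for safety and within strata, become visible.
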